#### 8.3.7.1. Infusion Reactions

Symptoms of a local infusion site reaction may include erythema, induration, pain, and edema. Worsening of CSU symptoms present at baseline does not necessarily constitute an infusion reaction, per the investigator's determination (see Section 8.3.6). If an infusion site event is reported, the AE will be recorded, and additional data will be provided to the sponsor in the eCRF.

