# 8.3.7. Adverse Events of Special Interest

Adverse events of special interest for this study include anaphylaxis, infusion reactions, and infections. If such AEs are reported, sites will be prompted to collect additional data as described in the following subsections.

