#### 8.3.7.2. Allergic Reactions and Hypersensitivity Events

All biologic agents carry the risk of systemic allergic/hypersensitivity reactions. Clinical manifestations of these reactions may include but are not limited to:

- skin rash
- dyspnea
- hypotension, and
- anaphylactic reaction (Sampson et al. 2006).

Participants with clinical manifestations of systemic allergic/hypersensitivity reactions should be treated per local standard of care. Additional data describing each symptom should be provided to the sponsor in the eCRF.

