#### Blood sample collection for systemic allergic/hypersensitivity events

In case of anaphylaxis or a systemic hypersensitivity event, additional blood samples should be collected as close as possible to the onset of the event. Follow-up samples should be obtained at the next regularly scheduled visit or 4 weeks after the event, whichever is later. The laboratory test results are provided to the sponsor via the central laboratory. See Appendix 10.2 for selected tests for which samples should be collected in the event of anaphylaxis or generalized urticaria.

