5.7.6. Special Safety Topics, including Adverse Events of Special Interest

In addition to general safety parameters, safety information on specific topics of special interest will also be presented. Additional special safety topics may be added as warranted. The topics outlined in this section include the protocol-specified AESI.

In general, for topics regarding safety in special groups and circumstances, patient profiles and/or patient listings, where applicable, will be provided when needed to allow medical review of the time course of cases/events, related parameters, patient demographics, study drug treatment and meaningful concomitant medication use. In addition to the safety topics for which provision or review of patient data is specified, these will be provided when summary data are insufficient to permit adequate understanding of the safety topic.

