5.7.6.4. Allergic Reactions/Hypersensitivities

A search will be performed using the current MedDRA version 20.0 SMQs to search for relevant events, using the following queries:

- Anaphylactic reaction SMQ (2000021)
- Hypersensitivity SMQ (20000214)
- Angioedema SMQ (2000024)

Events that satisfy the queries will be listed, by temporal order within patient ID, and will include SOC, PT, SMQ event categorization including detail on the scope (narrow or broad), reported AE term, AE onset and end dates, severity, seriousness, outcome, etc.

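### Infusion reactions are a named AESI, but the specific data prompt covers only infusion-site events and the SAP has no grouped infusion-reaction summary

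*Protocol*

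**What the plan says.** Protocol 8.3.7 sets the list: "Adverse events of special interest for this study include anaphylaxis, infusion reactions, and infections". It then promises added data for each: "If such AEs are reported, sites will be prompted to collect additional data as described in the following subsections".

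The subsections differ in scope.

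- **8.3.7.1, Infusion Reactions.** It describes local symptoms only: "Symptoms of a local infusion site reaction may include erythema, induration, pain, and edema". Its prompt is equally local: "If an infusion site event is reported, the AE will be recorded, and additional data will be provided to the sponsor in the eCRF". It gives no definition or time window for a systemic infusion reaction.
- **8.3.7.2, Allergic Reactions and Hypersensitivity Events.** For systemic allergic or hypersensitivity reactions it asks for symptom-level data: "Additional data describing each symptom should be provided to the sponsor in the eCRF". It also asks for samples: "In case of anaphylaxis or a systemic hypersensitivity event, additional blood samples should be collected as close as possible to the onset of the event".
- **8.3.7.3, Infections.** A dedicated eCRF page is required for every infection reported as an AE or SAE.

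On the analysis side, SAP 5.7.6 states: "The topics outlined in this section include the protocol-specified AESI". Its four subsections are hepatic tests, renal function, infections and allergic reactions/hypersensitivities. For the last, SAP 5.7.6.4 runs three standardised MedDRA queries (SMQs) and stops at a listing: "Events that satisfy the queries will be listed, by temporal order within patient ID". Infections, by contrast, get the number and percentage of participants by treatment group (SAP 5.7.6.3).

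**The concern.** The study drug is an antibody given by IV infusion every two weeks, and the sponsor itself chose infusion reactions as a topic of special interest. As worded, a systemic reaction around an infusion that the investigator does not regard as allergic (fever and chills, say) falls between the two subsections. If the extra data are not collected at the time, no analyst can rebuild them later.

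The SAP then has no place where infusion reactions, local or systemic, are counted together. Of the three AESIs, infections alone get a grouped count by treatment. A proof-of-concept study that is meant to inform dose selection in later studies (Protocol 4.2) could therefore end without a defined infusion-reaction rate per arm.

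**Working it through.** The plan states no figure on this point, so the check is mainly a comparison of texts, with one small calculation on what a grouped table could show.

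**1. Which prompt does each kind of event meet?**

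| Event | 8.3.7.1 prompt | 8.3.7.2 prompt |
|---|---|---|
| Local infusion-site reaction | yes | no |
| Systemic reaction, classed as allergic/hypersensitivity | no | yes, with blood samples |
| Systemic reaction, not classed as allergic | no | no |

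The gap is the third row.

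**2. What analysis does each AESI get under SAP 5.7.6?**

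| AESI | Output |
|---|---|
| Infections | n (%) by treatment, several groupings |
| Anaphylaxis | SMQ listing only |
| Infusion reactions | none |

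**3. What do the general tables add?** SAP 5.7.2 summarises all TEAEs by treatment, by preferred term within system organ class, with Fisher's exact test at both levels. SAP 5.7.2.1 and 5.7.2.2 tabulate SAEs and AE discontinuations by treatment. Reported reactions are therefore compared, but row by row. Three features limit these tables for infusion reactions:

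- Non-serious itching, hives and angioedema are not reported as AEs (Protocol 8.3.6, SAP 5.7.2), so these possible signs of a reaction may not reach the tables.
- SAP 5.7.2 assigns Visits 2 to 9 to Period 2 and Visits 10 to 16 to Period 3. The Schedule of Activities gives the first crossover infusion at Visit 9 (Week 12), and Visit 10 is at Week 13. A reaction to that infusion is counted in the preceding period or falls between the windows. For Sequence Group 2 it is the first active infusion.
- SAP 5.3.1 analyses safety by the intervention received within each period. SAP 5.7 analyses it by the product randomised at Week 0. Under the latter, Sequence Group 2 reactions to active drug in Period 3 would be labelled placebo.

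**4. Exposure.** The schedule has 6 infusions per period (Visits 2, 4, 5, 6, 7, 8, then 9, 11, 12, 13, 14, 15). With 60 randomised 3:1, Period 2 has 60 × 3/4 = 45 active and 15 placebo participants, or 45 × 6 = 270 and 15 × 6 = 90 infusions. Over both periods it is 60 × 6 = 360 of each. All assume that everyone completes.

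**5. What could a test show at 45 versus 15?** With 0 of 15 events on placebo, Fisher's two-sided p is 0.051 for 11 of 45 and 0.027 for 12 of 45. So 12 of 45 (27%) are needed for p ≤ 0.05. With a true placebo rate of 0%, power is P(X ≥ 12) for X ~ Binomial(45, p). The rates below are assumptions, not taken from the documents:

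| Assumed active rate | Power, one pooled group |
|---|---|
| 10% | 0.1% |
| 20% | 17% |
| 30% | 74% |

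If the 30% is split evenly over three preferred terms, each has a rate of 10% and power of 0.1%. Grouping helps at high rates. At low rates neither approach has power, and the value is a descriptive count.

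**The case against.** A reader might infer that systemic infusion reactions are never compared by treatment, or that no by-treatment summary of them exists. The documents do not support that. Every TEAE enters the tables and Fisher's tests of SAP 5.7.2. Protocol 7.1.1 says that study drug should be discontinued after a systemic hypersensitivity event or anaphylaxis, so those events should also appear in the discontinuation table of SAP 5.7.2.2.

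A reader might also infer that extra data are collected only for infusion-site events. That is true of 8.3.7.1 alone, since 8.3.7.2 provides eCRF data and samples for allergic systemic reactions. The general prompt in 8.3.7 is keyed to the AESI by name, and both schedule tables repeat that extra data are collected for AESIs. The eCRF itself is not among the documents, so its actual behaviour is unknown.

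Scatter over preferred terms is limited too, because Protocol 10.3.3 asks for the diagnosis rather than individual signs whenever possible. Protocol 2.3 judges the risk of cytokine release to be low. SAP 5.7.6 allows topics to be added as warranted, and listing rare hypersensitivity events for medical review is defensible in a small study.

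All of this stands, and it narrows the point. It does not close it: the general prompt in 8.3.7 defers to subsections that leave out the non-allergic systemic reaction, and SAP 5.7.6 does not contain the topic that it says it includes.

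**Conclusion.** The point holds as a mismatch between the AESI list, the data prompt and the SAP, with a cheap remedy. A systemic infusion reaction not classed as allergic or hypersensitivity meets neither specific prompt. Infusion reactions have no predefined grouped summary, and anaphylaxis and hypersensitivity hits have a listing without counts. Comparison by treatment exists only through individual preferred terms and system organ classes.

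The share of reactions affected cannot be sized, because the documents give no infusion-reaction rate and no split between allergic and other systemic events. The conclusion rests on reading 8.3.7 together with its subsections, as its own cross-reference requires. It does not rest on a claim that a test would detect a difference: at about 45 versus 15 that needs a rate near 30% on active drug with none on placebo.

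**What to change.** 1. **Protocol 8.3.7.1.** Change the data-collection trigger from an infusion site event to an infusion reaction (infusion-site or systemic, whether or not judged allergic), and align the eCRF guidance.
2. **SAP 5.7.6.** Add an infusion-reaction topic: events on that AESI eCRF, as participants n (%) by treatment actually received in each period. Assign each event by the infusion received, so that the Visit 9 infusion counts to Period 3. Reconcile the by-treatment rules of SAP 5.3.1 and 5.7 for this table. Keep it descriptive. Per-infusion rates are optional.
3. **SAP 5.7.6.4.** Keep the listing and add n (%) by treatment for each SMQ, narrow and broad.

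Counting every TEAE with onset on an infusion day is not advised as a definition: it would take in unrelated events and miss delayed reactions.

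The cost is one phrase in the protocol, a few more AESI forms for mild events and two descriptive tables. Dose date and time are already recorded (Protocol 6.4), and the SAP already uses AE onset. Patient management does not change.

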#### 8.3.7.2. Allergic Reactions and Hypersensitivity Events

All biologic agents carry the risk of systemic allergic/hypersensitivity reactions. Clinical manifestations of these reactions may include but are not limited to:

- skin rash
- dyspnea
- hypotension, and
- anaphylactic reaction (Sampson et al. 2006).

Participants with clinical manifestations of systemic allergic/hypersensitivity reactions should be treated per local standard of care. Additional data describing each symptom should be provided to the sponsor in the eCRF.

#### Blood sample collection for systemic allergic/hypersensitivity events

In case of anaphylaxis or a systemic hypersensitivity event, additional blood samples should be collected as close as possible to the onset of the event. Follow-up samples should be obtained at the next regularly scheduled visit or 4 weeks after the event, whichever is later. The laboratory test results are provided to the sponsor via the central laboratory. See Appendix 10.2 for selected tests for which samples should be collected in the event of anaphylaxis or generalized urticaria.

# 8.3.7.3. Infections

Completion of the Infection eCRF page is required for each infection reported as an AE/SAE. The sponsor will identify infections considered to be opportunistic based on the article by Winthrop et al. (2015) (Appendix 10.6).

# 8.3.8. Complaint Handling

Lilly collects product complaints on investigational medicinal products used in clinical trials in order to ensure the safety of study participants, monitor quality, and facilitate process and product improvements. Participants should be instructed to contact the investigator as soon as possible if he or she has a complaint or problem with the investigational medicinal product so that the situation can be assessed.

# 8.4. Treatment of Overdose

For the purposes of this study, an overdose of LY3454738 is considered any dose higher than the dose assigned through randomization.

The treatment for overdose is supportive care (see the IB for LY3454738).

# 8.5. Pharmacokinetics

#### Visits and times

At the visits and times specified in the SoA (Section 1.3), venous blood samples will be collected to determine the serum concentrations of LY3454738. The actual date and time (24-hour clock time) of dosing and sample collection will be recorded.

Blood samples for PK are requested to be collected at the specified times. However, deviations from the specified sampling times will not be considered protocol deviations as long as the samples are collected and the actual sampling time is recorded. It is essential that the actual times of doses and samples are recorded accurately on the appropriate forms.

#### Collection, handling, and storage of samples

Instructions for the collection and handling of blood samples will be provided by the sponsor. Samples will be analyzed at a laboratory approved by the sponsor and stored at a facility designated by the sponsor.

Concentrations of LY3454738 will be determined using a validated enzyme-linked immunosorbent (ELISA) assay method. Analyses of samples collected from placebo-treated participants are not planned.

# Additional and unused samples

A maximum of 3 additional samples for exploratory analyses such as bioanalytical method development or validation exercises may be collected at additional time points during the study if warranted and agreed upon between both the investigator and sponsor.

In the case of systemic allergic/hypersensitivity reactions, additional blood samples will be obtained for PK analysis (Section 8.3.7.2).

Any excess samples collected for PK testing may be pooled and used for exploratory analyses such as bioanalytical assay validation or cross-validation exercise.

# Blinding

Drug concentration information that may unblind the study will not be reported to investigative sites or blinded personnel.

# Sample retention

Samples collected to measure IP concentration will be retained at a facility selected by the sponsor or its designee. These samples will be retained for the purposes and maximum duration specified in Appendix 10.1, Section 10.1.12.

# 8.6. Pharmacodynamics

In addition to exploratory biomarker sample collections described below (Section 8.8), samples for other PD evaluations will be collected for exploratory analyses at the visits and times specified in the SoA (Section 1.3), where local regulations allow. These evaluations may include high-sensitivity C-reactive protein (hs-CRP), characterization of white blood cell differential counts, and soluble CD200R levels.

# 8.7. Genetics

A whole blood sample will be collected for pharmacogenetic analysis as specified in the SoA (Section 1.3), where local regulations allow.

#### Sample use

Samples will not be used to conduct unspecified disease or population genetic research either now or in the future. Samples will be used to investigate variable exposure or response to LY3454738 and to investigate genetic variants thought to play a role in CSU. Assessment of variable response may include evaluation of AEs or differences in efficacy.

Molecular technologies are expected to improve during storage period and therefore cannot be specifically named. However, existing approaches include whole genome or exome sequencing, genome-wide association studies, and candidate gene studies. Regardless of technology utilized, genotyping data generated will be used only for the specific research scope described in this protocol.

#### Confidentiality

All samples will be coded with the participant number. These samples and any data generated can be linked back to the participant only by the investigator site personnel. The sponsor will store the blood and/or deoxyribonucleic acid (DNA) samples in a secure storage space with adequate measures to protect confidentiality.

#### Sample retention

Samples will be retained at a facility selected by the sponsor or its designee. These samples will be retained for the purposes and maximum duration specified in Appendix 10.1, Section 10.1.12, or for a shorter period if local regulations and/or Ethical Review Boards (ERBs)/IRBs impose shorter time limits.

# 8.8. Biomarkers

Serum, plasma, whole blood RNA, and whole blood for nonpharmacogenetic biomarker research will be collected at the visits and times specified in the SoA (Section 1.3), where local regulations allow.

#### Sample use

Biomarker research is performed to address questions of relevance to drug disposition, target engagement, pharmacodynamics, mechanism of action, variability of participant response (including safety), and/or clinical outcome. Sample collection is incorporated into clinical studies to enable examination of these questions through measurement of biomolecules including DNA, RNA, proteins, lipids, and other cellular elements.

Samples will be used for research on the drug target, CSU disease process, variable response to LY3454738, pathways associated with CSU, mechanism of action of LY3454738, and/or research method or in validating diagnostic tools or assays related to CSU or to LY3454738.

#### Confidentiality

All samples will be coded with the participant number. These samples and any data generated can be linked back to the participant only by the investigator site personnel.

#### Sample retention

Samples will be retained at a facility selected by the sponsor or its designee. These samples will be retained for the purposes and maximum duration specified in Appendix 10.1, Section 10.1.12, or for a shorter period if local regulations and/or ERBs/IRBs impose shorter time limits.

# 8.9. Immunogenicity Assessments

#### Visits and times

At the visits and times specified in the SoA (Section 1.3), predose venous blood samples will be collected to determine antibody production against LY3454738. The actual date and time (24-hour clock time) of each sample collection will be recorded.

To aid interpretation of these results, a predose blood sample for PK analysis will be collected at the same time points.

#### Sample collection, handling, and use

Instructions for the collection and handling of blood samples will be provided by the sponsor.

Immunogenicity will be assessed by a validated assay designed to detect anti-drug antibodies (ADAs) in the presence of LY3454738 at a laboratory approved by the sponsor. Antibodies will be further evaluated for their ability to neutralize the activity of LY3454738, when available.

#### Sample retention

Samples will be retained at a facility selected by the sponsor or its designee. These samples will be retained for the purposes and maximum duration specified in Appendix 10.1, Section 10.1.12, or for a shorter period if local regulations and/or ERBs/IRBs impose shorter time limits.

# 8.10. Health Economics or Medical Resource Utilization and Health Economics

This section is not applicable.

# 9. Statistical Considerations

# 9.1. Statistical Hypotheses

The study will compare LY3454738 with placebo in adults with CSU. The primary study objective is to demonstrate superior efficacy of LY3454738 over placebo.

The primary comparison of interest is the mean change of the UAS7 from baseline to Week 12. Secondary comparisons include the mean change of the ISS7 and the HSS7 from baseline to Week 12 as well as the proportion of participants achieving a UAS7  $\leq 6$  at Week 12.

Efficacy comparisons will be made regardless of treatment discontinuation and without regard to changes to any background therapies. No adjustments for multiplicity will be made across the efficacy assessments.

# 9.2. Sample Size Determination

Assuming a 30% screen fail rate, approximately 85 participants will be screened to achieve 60 participants randomly assigned to study intervention for an estimated total of 52 evaluable participants.

The sample of 52 evaluable participants provides about 87% power to the primary endpoint. This calculation is based on a 2-sample t-test, assuming a mean change from baseline to Week 12 in the UAS7 for LY3454738 and for placebo of 17 points and 10 points, respectively, a standard deviation of 7 points for the change from baseline, and a 0.05 two-sided significance level.

# 9.3. **Populations for Analyses**

Population	Description
Entered	All participants who sign the informed consent form
Modified Intent-to-Treat (mITT)	All participants randomly assigned to study intervention and who take at
	least 1 dose of study intervention. Participants will be analyzed according
	to the intervention to which they were assigned.
Safety	All participants randomly assigned to study intervention and who take at
	least 1 dose of study intervention. Participants will be analyzed according
	to the intervention they actually received within each study period.
Pharmacokinetic (PK) Analysis	All participants randomly assigned to study intervention and who take at
	least 1 dose of study intervention and have PK data available.

The following populations are defined for this study:

# 9.4. Statistical Analyses

Statistical analysis of this study will be the responsibility of the sponsor or its designee.

Any change to the data analysis methods described in the protocol will require an amendment only if it changes a principal feature of the protocol. Any other change to the data analysis methods described in the protocol, and the justification for making the change, will be described in the statistical analysis plan (SAP) and clinical study report. Additional exploratory analyses of the data will be conducted as deemed appropriate.

The SAP will be finalized prior to unblinding. It will include a more technical and detailed description of the statistical analyses described in this section. This section is a summary of the planned statistical analyses of the most important endpoints including primary and key secondary endpoints.

